## **5 STUDY OBJECTIVES**

### **5.1 PRIMARY**

To assess the usability of the sarilumab pre-filled syringe with safety system (PFS-S) when administered to patients with active Rheumatoid Arthritis (RA)

### **5.2 SECONDARY**

To document the safety of sarilumab 150 mg q2w PFS-S and sarilumab 200 mg q2w PFS-S

## 6 STUDY DESIGN

### 6.1 DESCRIPTION OF THE PROTOCOL

This is a Phase 3, multicenter, worldwide, non-randomized, open-label, 1-arm, 12-week sub-study of the LTS11210/SARIL-RA-EXTEND study. The sub-study will only be performed in limited sites in selected countries.

Patients at participating sites who have been enrolled in the main study (LTS11210) for at least 24 weeks and are willing to participate in the sub-study will be enrolled in the sub-study. The entry into the sub-study (V101) will be at any scheduled visit in the main study from Visit 8 (Week 24) or after. Sarilumab 150 mg q2w PFS-S or sarilumab 200 mg q2w PFS-S will be used in the sub-study to replace the sarilumab 150 mg q2w PFS or 200mg q2w PFS used in the main study. At the entry into the sub-study (V101), the patients will be trained how to use the PFS-S, and the sub-study injection diary will be dispensed to replace the patient diary of the main study. All the procedures described in the sub-study are additional to the main study activities, unless specified to replace procedures in the main study.

The person performing each sub-study injection will respond to 3 questions related to PFS-S use on the injection diary (See [Section 9.1](#)) after each PFS-S injection. A “no” response to any question will be defined as a PTC. For any PTC, the Investigator will complete a PTC form and will send this PTC form together with the PFS-S that triggered this PTC back to the Sponsor according to a predefined process ([Section 12](#)). The patients should be instructed to keep any PFS-S associated with a PTC separately from other PFS-S, so it can be identified when returned to site at the end of sub-study.

For patients receiving sarilumab 200 mg q2w PFS-S the dose can be reduced any time during the sub-study duration if the main protocol defined criteria for dose reduction are fulfilled.

When the patients have completed the 12 weeks of the sub-study they will return to the clinic to complete Visit 102 in addition to the scheduled main study visit on that day. They will switch back to the main study and continue sarilumab PFS treatment.

If the patient chooses to end the participation in the sub-study during the sub-study duration but to continue in the main study the Visit V102 should still be completed.

If a patient discontinues Investigational Medicinal Product (IMP) permanently in LTS11210 during the sub-study, he/she should complete all procedures planned for V102 in the sub-study as well as the end of treatment (EOT) and post treatment follow-up visits in the main study (see flowchart in main study [Section 1.2](#)).

## **6.2 DURATION OF STUDY PARTICIPATION**

### **6.2.1 Duration of study participation for each patient**

Each patient will participate in the sub-study for a period of 12 weeks from the first sub-study visit (V101) to the final sub-study visit (V102). At the time of V101, eligible patients will start receiving sarilumab 150 mg q2w PFS-S or sarilumab 200 mg q2w PFS-S for 12 weeks as replacement of original sarilumab PFS in the main study and on top of the background disease modifying anti-rheumatic drugs (DMARDs) therapy, if any. There is no post-treatment follow-up specific to the PFS-S sub-study, as all patients will switch back to the main study at V102.

### **6.2.2 Determination of end of sub-study (all patients)**

The last on-treatment sub-study visit for patients who complete the sub-study will occur at Day 85 (Visit 102). The sub-study will be considered completed when the last sub-study patient has completed V102.

## **6.3 INTERIM ANALYSIS**

No interim analysis is planned.

## **6.4 STUDY COMMITTEES**

Please refer to the main study protocol.

## **7 SELECTION OF PATIENTS**

Approximately 120 patients active in the main study (LTS11210) are planned to be enrolled at selected sites in countries participating in the sub-study.

### **7.1 INCLUSION CRITERIA**

- I 01. Patients enrolled in the LTS11210 study who are receiving either sarilumab 200mg q2w PFS or sarilumab 150mg q2w PFS and who are able and willing to participate in this sub-study
- I 02. Patients who have been enrolled in the main study for at least 24 weeks
- I 03. Patients must sign a sub-study written informed consent prior to any sub-study related procedure

### **7.2 EXCLUSION CRITERIA**

There are no additional exclusion criteria to those defined in LTS11210.

## 8 STUDY TREATMENTS

### 8.1 INVESTIGATIONAL MEDICINAL PRODUCT(S)

#### **Investigational Medicinal Product**

Sarilumab, anti-IL-6R mAb (anti-interleukin 6 receptor monoclonal antibody)

#### **Pharmaceutical form**

1 mL long glass prefilled syringes with a needle safety shield (PFS-S) filled to a nominal injection volume of 1.14 mL with drug product at 131.6 mg/mL (150 mg) or 175 mg/mL (200 mg)

#### **Dose per administration**

- Single-use administration of sarilumab by PFS-S
- Dose of either 150 mg or 200 mg q2w

NOTE: Patients should continue to receive the same sarilumab dose as they have received in the main study, unless they fulfill main protocol defined criteria for dose reduction.

#### **Route and method of administration**

The route and administration method of sarilumab PFS-S used in the sub-study are same as sarilumab PFS used in the main study.

Each sub-study injection will be performed by the patient, or their caregiver. In exceptional circumstances (such as the 1st administration using PFS-S) the injection may be performed by the site staff. The patient or their caregiver will be trained on performing the injection with the PFS-S using a patient user instruction specific to the use of the PFS-S and a training PFS-S filled with sucrose together with an injection pad. This training must be documented in the patient's study file.

#### **Duration of administration of PFS-S**

12 weeks (6 injections)

### 8.2 NONINVESTIGATIONAL MEDICINAL PRODUCT(S)

NIMP received in the sub-study corresponds to NIMP received in the main study.

### 8.3 BLINDING PROCEDURES

Not applicable. This is an open-label study.

#### **8.4 METHOD OF ASSIGNING PATIENTS TO TREATMENT GROUP**

This is a 1-arm open-label sub-study, no randomization will be performed for the study.

At the sub-study entry (V101/D1), after the patient has given informed consent and the patient's eligibility has been confirmed, the site staff will contact the IVRS/IWRS in order to enroll the patient into the sub-study and to allocate the sub-study treatment kits. Either sarilumab 150 mg q2w PFS-S or sarilumab 200 mg q2w PFS-S will be allocated to each patient. The allocated dose will be the same as in the main study except if conditions for dose reduction are met.

The sub-study patients will continue to use the same patient number assigned during enrollment into the main study, which consists of 9 digits (3 digits indicating the country, 3 digits indicating the site and 3 digits indicating the patient)

#### **8.5 PACKAGING AND LABELING**

The IMP (sarilumab in PFS-S) will be provided in a patient treatment kit box. The kit will be labeled in accordance with the local regulatory specifications and requirements, along with content information, dosing instructions, and precautionary statement ("for clinical use only"). A sub-study treatment kit has specific labeling that distinguishes syringes in a treatment kit. They are labeled "Dose 1" and "Dose 2".

Packaging is in accordance with the administration schedule. The number of treatment kits allocated to the patient will provide sufficient medication until the next clinic visit. Additional treatment kits, to provide medication to patients under circumstances, such as a damaged kit, will be allocated by IVRS/IWRS when a "replacement treatment call" is made to IVRS/IWRS.

#### **8.6 STORAGE CONDITIONS AND SHELF LIFE**

The storage conditions and shelf life of sarilumab PFS-S used in the sub-study are the same as sarilumab PFS used in the main study.

#### **8.7 RESPONSIBILITIES**

Site personnel responsibilities in the sub-study are the same as in the main study.

##### **8.7.1 Treatment accountability and compliance**

The completed injection diary should be returned by the patient at the end of the sub-study (V102/D85).

All PFS-S medication treatment kits (with all used or unused PFS-S) must be returned by the patient at the end of the sub-study (V102/D85).

The study coordinator will track treatment accountability/compliance of PFS-S by comparing the information recorded in the patient diary with the number of returned treatment boxes and used/unused PFS-S and fill in the appropriate page of the patient treatment log.

The monitor in charge of the study will then check the data entered on the e-CRF IMP administration page by comparing them with the IMP that has been retrieved and the patient treatment log.

### **8.7.2 Return and/or destruction of treatments**

All used and unused PFS-S will be collected by the study site at V102/D85. All used PFS-Ss for which a PTC was reported will be returned to the Sponsor.

At selected sites, used PFS-S which functioned normally with no PTC will be returned to the Sponsor as well.

Used PFS-S with complaints regarding labeling, packaging or a cosmetic defect of the PFS-S, will not be further investigated as a part of the sub-study.

A detailed treatment log of the returned PFS-S returned to the sponsor will be established with the Investigator (or the pharmacist) and countersigned by the Investigator and the monitoring team.

### **8.8 CONCOMITANT MEDICATION**

Prohibited and permitted concomitant medication is defined in the main study protocol.

## 9 ASSESSMENT OF INVESTIGATIONAL MEDICINAL PRODUCT

### 9.1 PRIMARY ENDPOINT

The primary endpoint is the number of validated PFS-S-associated PTFs. A PTF is defined as any PTC related to the use of the PFS-S which has a validated technical cause. A PTC is defined as any patient- or healthcare provider-reported complaint regarding the use of the PFS-S syringe and collected via the completion of the injection diary.

The injection diary will include specific questions about PTCs. The person performing each sub-study injection will record the answers to these questions in the diary each time he/she performs an injection with a PFS-S.

The questions include:

1. Were you able to remove the cap?
  - a) Yes
  - b) No
    - i If no, please describe / explain:
2. Was the needle safety system activated?
  - a) Yes
  - b) No
    - i If no, please describe / explain:
3. Did the safety system entirely cover the needle?
  - a) Yes
  - b) No
    - i If no, please describe / explain:

At Visit 102, the Investigator will review the diary, confirm with the patient whether there were any problems associated with the use of PFS-S either during drug administration or otherwise, and record the responses in the e-CRF.

If the answer is “no” to any of the questions stated in the diary, the patients will be asked to provide further details of the complaint and a PTC form will be completed by the investigator. The PTC form and the PFS-S associated with PTC will be sent to the Sponsor following the process defined in [Section 12](#). The sponsor will validate or invalidate the occurrence of a PTF. If the PTF is ruled out the event is considered as a failed drug delivery (FDD) and is defined as patient’s failure to administer the full dose at a given attempt.

In addition, another question will be asked in the diary to confirm whether the person who performed the injection was trained:

4. Was the person who performed the injection the person who was trained by the site staff?
  - a) Yes
  - b) No

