## 4 INTRODUCTION AND RATIONALE

### 4.1 PRE-FILLED SYRINGE WITH SAFETY SYSTEM (PFS-S)

Sarilumab has been delivered via prefilled syringes (PFS) in most of the Phase 3 studies.

[figure not shown]
The pre-filled syringe with safety system (PFS-S) is a modified version of the prefilled syringe aimed at preventing needle stick injury by either the patient or by a caregiver (professional or non-professional) performing the administration. The “safety system” consists of a sharps injury prevention feature, which can be described as a sheath that automatically covers the needle once the injection is completed and thus prevents needle stick injury and re-use.

Compared to PFS, PFS-S also includes:

[figure not shown]
- a rigid needle shield that encloses the soft rubber needle shield covering the needle
- a finger flange with an ergonomic design and a large piston rod

The following figures show the unused and used PFS-S. At the end of the injection when the plunger rod has been pushed into the syringe as far as it will go, the needle safety shield is activated which can be seen as the syringe is pulled away from the skin.

*Unused syringe*

*Used syringe with activated needle safety shield*

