## **9.2 SECONDARY ENDPOINTS**

### **9.2.1 Device related endpoints**

- Number of PFS-S-associated product technical complaints (PTCs).
- Number and percentage of patients with PTFs
- Number and percentage of patients with PTCs
- Number and percentage of patients with FDDs

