## ***Primary endpoint***

The primary endpoint is the number of validated PFS-S-associated PTFs.

The injection diary will include specific questions about PTCs. The person performing each sub-study injection will record the answers to these questions in the diary each time he/she performs an injection with a PFS-S.

The questions include:

1. Were you able to remove the cap?
  - Yes
  - NoIf no, please describe / explain:
2. Was the needle safety system activated?
  - Yes
  - NoIf no, please describe / explain:
3. Did the safety system entirely cover the needle?
  - Yes

- No  
If no, please describe / explain:

At Week 12 (Visit 102), the Investigator will review the diary, confirm with the patient whether there are any problems associated with the use of PFS-S and record the responses in the e-CRF.

If the answer is “no” to any of the questions stated in the diary, the patients will be asked to provide further details of the complaint and a PTC form will be completed by the investigator. The PTC form and the PFS-S associated with PTC will be sent to the Sponsor following the pre-defined process. The sponsor will validate or invalidate the occurrence of a PTF. If the PTF is ruled out, the event is considered as a failed drug delivery (FDD) that is defined as patient’s failure to administer the full dose at a given attempt.

In addition, another question will be asked in the diary to confirm whether the person who performed the injection was trained:

4. Was the person who performed the injection the person who was trained by the site staff?
  - Yes
  - No

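### In the PFS-S sub-study, a complaint without a technical cause becomes a failed drug delivery with no check on the dose, so a completed injection with incomplete needle coverage is misclassified

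*Protocol*

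**What the plan says.** Protocol Appendix R Section 6.1 sets the trigger: "The person performing each sub-study injection will respond to 3 questions related to PFS-S use on the injection diary", and "A “no” response to any question will be defined as a PTC". Section 9.1 lists the questions. The first concerns cap removal, the second activation of the needle safety system, and the third whether the needle was entirely covered. A fourth item asks only whether the injector was the person trained by site staff.

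For each complaint the investigator completes a form, the syringe goes to the sponsor, and the sponsor confirms or rejects a technical failure. Section 9.1 then gives the only stated classification rule: "If the PTF is ruled out the event is considered as a failed drug delivery (FDD"). The FDD is defined there as the patient's "failure to administer the full dose at a given attempt". SAP Appendix K, under Primary endpoint, has the same rule: "If the PTF is ruled out, the event is considered as a failed drug delivery (FDD").

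Appendix R Section 9.2.1 lists "Number and percentage of patients with FDDs" among the secondary device endpoints, and SAP Appendix K does the same. Appendix R Section 4.1 describes the mechanism: "when the plunger rod has been pushed into the syringe as far as it will go, the needle safety shield is activated".

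**The concern.** An FDD is defined by a dose outcome but assigned by elimination: once a technical cause is rejected, the event is taken to be an incomplete dose. Failing to find a device fault does not show that the dose was incomplete. A user can leave the needle partly exposed after giving everything in the syringe. That is a needle-protection problem, which is what the safety system is meant to prevent, and it would appear under a label about missed dosing.

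A reader of the sub-study report would take the percentage of patients with FDDs as a delivery failure rate attributable to users. To the extent that coverage complaints feed into it, the figure overstates delivery failures and hides the sharps-protection complaints among them.

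**Working it through.** **Step 1. Rule set against device description.** Take a complaint with the PTF ruled out and follow each answer pattern through Appendix R Sections 4.1 and 9.1.

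| Answers | What the device description implies about the dose | Class under the rule |
|---|---|---|
| Cap not removed | Injection probably not given | FDD, plausible |
| Shield not activated | Plunger probably not fully depressed | FDD, plausible |
| Shield not activated, needle not covered | As above; the uncovered needle follows from non-activation | FDD, plausible |
| Shield activated, needle not entirely covered | Plunger fully depressed, injection completed | FDD, contradicts the definition |

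The last row is the demonstrable error. Premature activation through a device fault would be a technical cause and hence a PTF, and this row requires that a PTF has been ruled out.

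**Step 2. The plan's own injection count.** Inputs from Appendix R Section 11.1: 120 patients, up to 6 injections each, 5% drop-out.

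- Patients: 120 × 0.95 = 114
- Injections: 114 × 6 = 684, against the stated figure of about 680. It reproduces.

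**Step 3. Size under assumption.** The documents give no complaint rate. Let p be the assumed proportion of injections with the last-row pattern, independent across the 6 injections of each of 114 patients.

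- Wrong FDD events = 684 × p
- Patients with at least one = 114 × [1 − (1 − p)^6]

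| Assumed p | Wrong FDD events | Patients affected | Percentage of 114 |
|---|---|---|---|
| 0.1% | 0.7 | 0.7 | 0.6% |
| 0.25% | 1.7 | 1.7 | 1.5% |
| 0.5% | 3.4 | 3.4 | 3.0% |
| 1% | 6.8 | 6.7 | 5.9% |
| 2% | 13.7 | 13.0 | 11.4% |

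If the complaints clustered within patients, fewer patients would be affected. In the extreme, with p = 2% and all six injections of a patient affected together, 13.68 / 6 = 2.28 patients, or 2.0% of 114. With an incomplete dose required for an FDD, every row becomes zero.

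**The case against.** The case on the other side is substantial, and most of it stands.

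- **Technical failures that stop delivery are not FDDs.** A reader might infer that the endpoint therefore misses true delivery failures. The documents do not support this. The definition concerns the patient's failure, so PTF and FDD separate product causes from user causes. Technical failures are the primary endpoint and are also reported by patient.
- **The diary does not ask about the dose directly.** A reader might infer that it holds no information on delivery. That goes too far: failure to remove the cap and failure to activate the shield are reasonable proxies for non-delivery. An injection stopped early should leave the shield unactivated and so be picked up by the second question.
- **A coverage complaint always means a completed injection.** This does not follow either. The needle is also uncovered when the shield never activated. The contradiction needs activation confirmed and coverage denied.
- **FDD events equal complaints minus technical failures.** The text does not establish this identity. Appendix R Section 8.7.2 excludes labelling, packaging and cosmetic complaints from investigation, and inconclusive cases are not addressed.
- **Dose information exists elsewhere.** A negative answer requires an explanation and a complaint form, the investigator asks about problems at Visit 102, and Section 8.7.1 refers to an e-CRF administration page. This is true, but no visible rule uses any of it to decide whether an event is an FDD.
- **The process figure in Appendix R Section 12 is not shown.** Its legend includes FDD, so it may hold a further step. The written rule in both documents has none.
- **Impact is limited.** FDD is one of four secondary device endpoints in a single-arm, descriptive sub-study, and complaint and failure counts are reported beside it. This lowers the stakes but does not make the classification correct.

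**Conclusion.** The point holds for one answer pattern. Both documents assign a dose outcome without using dose information. When the shield activated, the needle was not entirely covered and a PTF was ruled out, the result contradicts the FDD definition. The endpoint affected is the number and percentage of patients with FDDs; the primary endpoint is untouched.

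The size is unknown because no complaint rate is given. Over an assumed 0.1% to 2% of 684 injections it is about 0.7 to 13.7 events and 0.6% to 11.4% of patients. The patient percentages rest on independence across six injections in 114 patients, and they bound the inflation from above, since a patient who also has a genuine FDD is counted anyway. The conclusion further assumes that the device works as Section 4.1 describes, that full plunger travel means the dose was given, and that the figure in Section 12 adds no dose check.

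**What to change.** In Protocol Appendix R Section 9.1 and SAP Appendix K, count an FDD only when the PTF is ruled out and an incomplete dose is documented. The source can be the complaint form, the e-CRF administration page, or one added diary or form item asking whether the full dose was delivered. Report the other cases in their own category: PTC without technical cause, full dose given. State how cases with unknown dose status or an inconclusive technical review are handled. If the process figure in Section 12 already contains a dose check, put it into the text of both documents.

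The cost is one form item or a short derivation from data already collected, plus the wording changes. The FDD count will be lower wherever such complaints occur. The complaint and technical failure endpoints do not change.

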## **9.2 SECONDARY ENDPOINTS**

### **9.2.1 Device related endpoints**

- Number of PFS-S-associated product technical complaints (PTCs).
- Number and percentage of patients with PTFs
- Number and percentage of patients with PTCs
- Number and percentage of patients with FDDs

### **9.2.2 Safety endpoints**

- Adverse events related to PTCs

Note: adverse events, laboratory values, vital signs, and electrocardiograms (ECG), assessed as part of the main LTS11210 study will not be described for the sub-study. If any adverse event reported during the sub-study is considered linked to a PTC by the investigator the potential link with the PTC should be specified in AE/SAE verbatim. If any laboratory or ECG abnormality or vital signs finding reported during the sub-study is considered clinically significant and linked to a PTC by the investigator an adverse event needs to be reported and the potential link with the PTC should be specified in AE/SAE verbatim. In addition a PTC of the PFS-S must be reported to the sponsor on a PTC form.

